4 STUDY DESIGN

4.1 Study Overview

Definition of Maximum Tolerated Dose (MTD)

In this modified Continual Reassessment Model (CRM) approach, the MTD is defined as the dose with a toxicity level closest to the target toxicity level of 25%. The CRM final MTD estimate is that dose that would have been given to the (N+1)st patient in the trial.

Definition of Dose Limiting Toxicity (DLT)

- a) A serious adverse event with causality of at least "Possibly" related to the study drug or
- b) A non-serious adverse event rated as at least moderate and "Possibly" related to the study drug
- c) The event that the subject experiences any of the following psychiatric symptoms
 - i) Visual hallucinations
 - ii) Humming or buzzing noises
 - iii) Sensations of sinking, body vibrations or waviness of the environment

- d) The event that the subject develops any of the following changes in vital signs within 6 hours following administration of study drug:
 - i) Symptomatic hypotension, or > 20% decrease in systolic blood pressure (SBP) from pre-dosing and an absolute SBP < 90; or
 - ii) Symptomatic hypertension, or > 20% increase in SBP or diastolic blood pressure (DBP) from predosing and absolute SBP > 170 or DBP > 95;
 - iii) New onset tachycardia (heart rate >100 bpm) and >20% increase from pre-dosing; or symptomatic bradycardia (heart rate <60 bpm) and > 20% decrease from pre-dosing.

Relationship	Attribution	Description
Unrelated to investigational drug	Unrelated	AE is clearly NOT related to intervention
	Unlikely	AE is doubtfully related to intervention
	Possible	AE may be related to intervention
Related to investigational drug	Probable	AE is likely related to intervention
	Definite	AE is clearly related to intervention

Table 1. Causal relationship between adverse event and investigational drug

Dose Escalation Rules

Generally, the CRM starts by selecting a target dose-limiting toxicity rate and a mathematical model assumed to govern the relationship between dose and toxicity; the prior dose-toxicity curve. After outcomes are observed (i.e., a patient experiences a DLT or not), the dose-toxicity curve is refit incorporating the latest outcome. The next dose assigned is that which is most likely to be associated with the target toxicity level (the MTD). At every step, the next patient is assigned the dose estimated to be nearest to the MTD.

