While the "3 + 3" design is the most commonly employed dose finding design, the CRM is generally accepted by statisticians as superior due to two main advantages: (1) the CRM provides a mechanism for stopping at a specified toxicity level, whereas the targeted toxicity rate for the MTD from the "3 + 3" design is necessarily in the range of 16%-33%, and (2) the CRM is more efficient; it can establish the MTD more accurately and precisely from fewer patients and it minimizes the number of patients treated at unsafe doses. Initial criticisms of the CRM, largely that unsafe escalation could occur too quickly, have been addressed by modifications to the original approach. Our implementation of the CRM will include modifications that prohibit steep dose escalations and will include the standard safety considerations of the traditional designs.

We will implement a series of precedented safety modifications to the original CRM design suggested by O'Quigley et al. in order to ensure subject safety. The first modification will be to start dosing from the

Confidential

lowest dose, far below the expected MTD, instead of starting at the prior MTD estimate (Wheeler 2019). Secondly, we will not skip untested dose levels when escalating doses in order to reduce the number of subjects exposed to potentially toxic doses. However, we can skip doses when de-escalating if the CRM recommends doing so (Wheeler 2019). Lastly, we will enforce coherent dose-escalation, where if the last patient has a DLT, the next patient will not receive a dose higher than that of the last patient, even if the model recommends it (Faries D 1994). These modifications are simple to implement and help to prevent overdosing subjects.

Dosing Design

We will employ the CRM with the following design parameters:

- a. The target dose limiting toxicity rate is 25%.
- b. 7 pre-defined dose levels: 100mg, 200mg, 300mg, 500mg, 700mg, 900mg and 1200mg with assumed prior toxicity rates of 2%, 5%, 10%, 20%, 30%, 50% and 65%.
- c. Model for dose-toxicity:
 - 1. A maximum of 40 evaluable patients. We do not plan to implement any stopping criteria (other than for toxicity). In the absence of DLTs we plan to enroll all 40 patients in order to increase the precision of the estimated MTD.

Rationale for Dose Determination

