Human data on oral harmine administration are limited and of poor quality, as noted above. Briefly, there is only one study that employed oral doses in the range of 20 to 960 mg (Pennes et al., 1957). No subject had any adverse visual hallucinations. Some subjects (number uncertain) experienced "nausea, vomiting, slow coarse spontaneous tremor, 'waviness' of the environment, 'sinking' sensations of the body, subjective sense of body vibration, and subject numbness accompanied by reduced sensitivity to light touch and pinprick". These effects were apparently observed only in "some subjects" and only "occurred with oral doses higher than the threshold of 300.0-400.0 mg." In addition, the Callaway Ayahuasca study (Callaway et al., 1999) administered harmine in the Ayahuasca "tea" at the dose of 3.4 mg/kg (range 204-306 mg). Callaway et al. noted that the effects of this dose of harmine (along with other ingredients of Ayahuasca) was perceived to be mild. Thus, based on this limited data, doses below 200 mg are likely safe, and single oral doses as high as 1000 mg may also be safe and free of significant adverse effects For this reason, and an added layer of caution, we have elected to initiate dosing at 100 mg which is less than half of the lower dose range in Callaway study. The upper level of dose range (1200 mg) is 4-times that of the highest dose of Callaway study.

In terms of selecting the number of doses tested between the established minimum (100 mg) and maximum (1200 mg) dose, the most important statistical consideration is whether the doses and dose range under investigation are likely to allow an accurate MTD estimate. In general, it is recommended that phase I studies contain between 2 and 12 dosing levels (Penel and Kramar, 2013); more levels generally allow for a more accurate determination of the MTD. Based primarily on clinical data, together with the available pre-clinical safety data, and utilizing established methods for defining the incremental sequence of a range of doses (Le Tourneau et al., 2009), our study protocol specifies the following 7 oral harmine dose levels to be tested according to the dose escalation model described below: 100 mg, 200 mg, 300 mg, 500 mg, 700 mg, 900 mg and 1200 mg.

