We will assign a prior probability distribution to the model parameters, assigning a prior probability of DLT at each dose based on the available data (Legedza, 2001). In order to minimize risk, we will implement a common modification to the CRM such that the first patient treated in the study will be treated at the lowest available dose (e.g., 100 mg) regardless of the prior distribution (Goodman et al, 1995). The study will end when either the maximum number of allowable patients treated per protocol is reached (see below), or it will end early in the event that the probability that the next 10 patients to be dosed in the trial will be given the same dose level, regardless of DLT outcomes observed exceeds 90% (Zohar and Chevret, 2001).

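### The MTD rule always returns one of the seven doses, so 100 mg would usually be named even at a DLT rate of 40% or more, unless a toxicity stop that the available text mentions but does not define intervenes

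*Combined protocol and SAP*

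**What the plan says.** Under Definition of Maximum Tolerated Dose, Section 4.1 states that "the MTD is defined as the dose with a toxicity level closest to the target toxicity level of 25" per cent, and adds: "The CRM final MTD estimate is that dose that would have been given to the (N+1)st patient in the trial". Dosing Design lists seven levels from 100 to 1200 mg, with assumed DLT rates of 2, 5, 10, 20, 30, 50 and 65%, and at most 40 evaluable volunteers.

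On stopping, Dosing Design item c says "We do not plan to implement any stopping criteria (other than for toxicity"). The escalation text promises modifications that "will include the standard safety considerations of the traditional designs". It then lists three: start at the lowest dose, do not skip untested levels when escalating, and do not escalate straight after a DLT.

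The synopsis (Primary Analysis Plan) and the statistical section before Section 16 give two ways to end: the maximum number treated, or an early end when "the probability that the next 10 patients to be dosed in the trial will be given the same dose level" exceeds 90%. Neither place lists a toxicity stop.

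**The concern.** Choosing the nearest of seven doses cannot give the answer that none of them is tolerable. When every dose lies above 25%, the lowest is nearest, however far above target it is. The three listed modifications restrain escalation and do nothing at the bottom level. The convergence stop has no toxicity condition, so it would end the trial early by confirming 100 mg.

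Section 3.1 says the MTD is to inform the recommended phase II dose. A trial in which 100 mg caused DLTs well above target could therefore hand on 100 mg as the maximum tolerated dose. It could also dose up to 40 healthy volunteers, who have no expected direct benefit, on the way there.

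**Working it through.** **Inputs from the plan.** Target 25%; the seven doses and prior rates above; start at 100 mg; no skipping upward; no escalation after a DLT; maximum 40. Section 4.1 (Choice of model) gives an empiric model, while the synopsis and statistical section give a logistic model with intercept 3, so both were run. The plan gives no operating characteristic for this situation, so there is no figure of its own to reproduce.

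**Assumed.** The spread of the parameter prior is not stated. Normal priors on the log parameter with SD from 0.5 to 1.34 were tried. True curves start at a chosen 100 mg rate and are flat or rising.

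**Step 1, the rule itself.** MTD = the level k that minimises |p_k − 0.25|. If p_1 ≥ 0.25 and rates do not fall with dose, then |p_k − 0.25| = p_k − 0.25 ≥ p_1 − 0.25 for every k, so level 1 is chosen. The distance is 0.40 − 0.25 = 0.15 at a true 40% and 0.50 − 0.25 = 0.25 at 50%. No distance is too large.

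**Step 2, the extreme case.** With a DLT in every volunteer (empiric model, SD 1.34), the estimated rate at 100 mg is 0.47 after 1 volunteer, 0.67 after 3 and 0.94 after 40. The rule selects 100 mg each time.

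**Step 3, simulation with 40 dosed and no toxicity stop.** Empiric model: p_k = s_k^exp(a), where s_k is the prior rate. Logistic model: logit p_k = 3 + exp(a)·d_k, with d_k = logit(s_k) − 3; for 100 mg, d_1 = −3.892 − 3 = −6.892.

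| True rate at 100 mg | 100 mg named, SD 0.75 or 1.16, rising curves | Full range, including SD 0.5 and flat curves | Mean DLTs in 40 |
|---|---|---|---|
| 40% | 89-100% | 64-100% | about 16-18 |
| 50% | 99-100% | 94-100% | about 20-21 |

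In the remaining trials a higher dose was named. No trial ended without a named dose.

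**Step 4, with the convergence stop (SD 0.75 or 1.16).** 100 mg is named in 92-100% of trials at a true 40% (mean 7-17 dosed) and in 99-100% at 50% (mean 4-10 dosed).

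**Step 5, an example check.** After at least 3 volunteers at 100 mg, stop if P(rate > 25%) > 0.95. With x DLTs in n at 100 mg and a Beta(0.5, 1.5) prior (mean 0.5/2 = 25%), the posterior is Beta(0.5 + x, 1.5 + n − x). The tail probability is 0.984 at 3/3, 0.956 at 3/4, 0.968 at 4/6, 0.959 at 5/9, 0.954 at 6/12 and 0.952 at 7/15. The check therefore stops at 3 DLTs in 3-4, 4 in 5-6, 5 in 7-9, 6 in 10-12 and 7 in 13-15.

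Without the convergence stop, and with SD 0.75 or 1.16, it fires in 92-98% of trials at a true 50%, 62-77% at 40% and 21-36% at 30%. Over all runs it fires in about 7-17% at exactly 25%. In the runs under the plan's prior rates it never fired. At a true 50%, mean exposure falls from 40 to about 12-21 volunteers.

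**The case against.** **A reader might infer that the trial has no toxicity stop.** The documents do not support that. Item c of Dosing Design expressly keeps one, and the text between Section 13 and the safety-monitoring text was not in the copy reviewed. That is a natural place for a halting rule and for what is concluded when it is met. The figures in Steps 3 and 4 therefore describe a design in which the stop is absent or never fires. What stands is narrower: the available text does not define the stop, and the two places that list how the trial ends leave it out.

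**A reader might infer that 100 mg is likely to be too toxic.** The plan points the other way. Its prior is 2%, so 40% is 20 times the assumption, and it states that "doses below 200 mg are likely safe". Oral reactions in the older study were placed above 300-400 mg. Section 4.2 of the background reports vomiting in 1 of 15 volunteers at about 253 mg (exact 95% upper limit 32%, for that one symptom). Against this, the plan concedes: "Human data on oral harmine administration are limited and of poor quality". Its DLT definition is also broad: the listed psychiatric symptoms count without a severity or causality requirement.

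**A reader might infer that naming 100 mg is wrong at any rate above 25%.** It is not. At 30%, 100 mg is the correct answer under the nearest-dose definition. The plan states no unacceptable rate. The 40% used here is a reviewer's choice, above the band the plan calls "necessarily in the range of 16%-33" per cent for the 3+3 design, which this trial does not use.

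**The practical harm is limited.** Suspected DLTs are formally adjudicated, amendments for immediate hazards are allowed (Section 17.1), and 16-20 DLTs in 40 volunteers would be visible beside any named dose. All of that stands. It lets people step in, but it does not change which dose the written rule reports.

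**Conclusion.** The point holds in a limited form, as a minor one. The MTD definition, together with the two ending conditions in the synopsis and statistical section, always yields a dose. If 100 mg truly had a DLT rate of about 40% or more, it would be named in roughly 64-100% of trials at 40% and 94-100% at 50%, unless the toxicity stop intervened. The width at 40% comes mainly from the unstated parameter prior and the shape of the true curve. The direction does not depend on either, or on which of the two working models is used. Whether the gap is one of substance or only of cross-reference depends on the missing page.

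**What to change.** 1. **Ending conditions (synopsis, Dosing Design item c, statistical section).** List the toxicity stop in all three places and state that it takes precedence over convergence. Cross-refer to its definition if the protocol already has one. If not, adopt a rule such as the Step 5 check, with the cut-off confirmed by simulation.
2. **MTD definition (Section 4.1).** Add: *If the toxicity stop is met at 100 mg, no dose is named; the result is that 100 mg was not shown to be tolerated.*

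Do not go further and withhold 100 mg whenever convergence ends the trial there. With result wording that places the MTD at or below 100 mg, that would discard a correct MTD in 30-76% of trials at exactly 25%. It could also report, falsely, that the MTD is not above 100 mg when the true 100 mg rate is low: 0-2% of trials under the plan's prior rates and 0-11% if 100 mg is at 5%.

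**Cost.** Two or three sentences, plus a simulation if no rule exists yet. With the example check and no convergence stop, about 7-17% of trials stop early when 100 mg sits exactly at 25% and is the MTD by definition. About 0% do under the plan's prior rates. The check is not complete protection: 100 mg is still named in about 18-35% of trials at a true 40%. Raising the cut-off to 0.975 lowers early stops at 25% to 5-10%, but lowers detection at 40% to 53-66%.

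**Dependence on the convergence stop.** If that stop is kept, it is often met at 100 mg before the check can fire. 100 mg then remains named in 79-100% of trials at 40% and 75-100% at 50%. Precedence must therefore be more than a tie-break. The sponsor should either follow Section 4.1 and drop the convergence stop, or include it in the simulation that sets the cut-off.

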As mentioned previously, harmine has been administered via oral, subcutaneous, and intravenous route²¹. In one study of physically healthy patients with mental illness, mostly in age group of 18-35 years, 11 patients were given oral harmine in dose range 20-960 mg, 6 patients were given subcutaneous harmine between the

Confidential

doses of 40-70 mg, and 11 patients were given intravenous harmine in between the doses of 100-300 mg²¹. Authors report that some patients got more than one dose of harmine (specifics are unclear). While authors report visual hallucinations with intravenous route, which was administered over 20-30 minutes, they reported that harmine was not hallucinogenic by oral or subcutaneous routine. In addition to visual hallucinations that occurred only when eyes were closed, authors reported the following adverse reactions with harmine: "nausea and vomiting, slow, coarse, spontaneous tremor of the extremities of an 'extrapyramidal' appearance; humming and buzzing noises; 'waviness' of the environment; 'sinking' sensations of the body; subjective sense of body vibration; and subject numbness that was accompanied by objective evidence of reduced sensitivity to light touch and pinprick." However, the authors reported, "These reactions, plus all the preceding, occurred in almost every patient with the intravenous route; and (except for hallucinations) some occurred with oral dosages higher than the threshold of 300-400 mg. The reactions were generally more intense by the former route".

There were no changes in heart rate or blood pressure reported for the group receiving oral administration²¹. However, bradycardia and hypotension occurred with all doses of intravenous harmine, limiting maximum dosage to 300 mg intravenously. With the intravenous administration, on average there was a decrease in pulse rate of 18 beats/minute and in blood pressure of 16mm mercury. Recovery occurred in about 30 minutes.

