2.2 Risk / Benefit Assessment

Risks to Subjects:

1) Screening evaluation

The risks and discomforts of the screening and baseline evaluations are minimal. No discomfort is expected to be associated with the physical examination or the clinical interview. Venipuncture may result in pain and/or bruising. In addition, there is a slight possibility of infection.

2) Harmine Administration

Anticipated side effects include the following; nausea, vomiting, slow, coarse, spontaneous tremor of the extremities, humming and buzzing noises, 'waviness' of the environment, 'sinking' sensations of the body, subjective sense of body vibration, numbress and reduced sensitivity to light touch.

Blood pressure and heart rate are anticipated to decrease by an average of 16mm and 18 beats/minute, respectively. Recovery should be observed after 30 minutes.

The study team will closely monitor possible drug-related DLTs, which are defined as 1). Any serious adverse event with causality of at least "Possibly" or any moderate or severe adverse event with causality of at least "Possibly" based on FDA guidelines and MSSM Adverse Event tracking form, or 2). The event that the patient's systolic or diastolic blood pressure (BP) or heart rate (HR) changes by greater than 20% relative to baseline values.

3) Questionnaires

Completing the questionnaires does not pose any risks. It might be a little tedious to repeat the same questionnaires over time. Participants may choose to decline to answer certain items and may stop testing at any point during the test session.

4) Intravenous catheter insertion

The insertion of the IV catheter may cause momentary discomfort. To minimize this, only experienced DAC personnel will perform the procedures involved.

5) Privacy risks

There always exists the potential risk for loss of private information. However, there are procedures in place to minimize the risk.

Potential Benefits to Subjects

No direct benefits may result from study participation. All participants will receive without cost an extensive psychiatric and medical evaluation. All participants will receive compensation for their participation in the study.

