9.3 Follow-up/Study Exit (V2)

Post-Baseline: approximately 24 hours after the oral dose

- a) Brief physical and interval medical history
- b) Update AE and con-med log
- c) Collect blood sample
 - a. 10 mL plasma
 - b. 3-5mL serum
- d) Clinical Scales/Self-Reports
 - a. C-SSRS
 - b. BPRS
 - c. POMS
 - d. PRISE
 - e. PSS
 - f. VAS

Study exit: Physician assessment followed by decision for discharge using standardized assessment scale

Time	Procedures
-90 min	 Subject arrives at Infusion Suite or CRU Name and number for escort home is collected Vitals* Urine tests: Drug abuse screen, Urinalysis, Pregnancy test (if applicable) Study doctor confirms 8-hour NPO Study doctor confirms adherence to low tyramine diet for past 72 hours Clinical assessments C-SSRS BPRS POMS PRISE PSS VAS Insertion of Hep-lock Baseline plasma and Serum sample: 1 ETDA and 1 SST
-10 min	 Pre-treatment baseline of vital signs: vital signs will

Table 2. Treatment Visit (Visit 1) Procedures

	be taken following 5 minutes of rest, with the average of two taken 5 minutes apart.
0 min	 Oral Administration of Harmine
+30 min	 Vital signs PRISE VAS Plasma and Serum sample: 1 ETDA and 1 SST
+60 min	 Vital signs PRISE VAS Plasma and Serum sample: 1 ETDA and 1 SST
+90 min	 Vital signs PRISE VAS Plasma and Serum sample: 1 ETDA and 1 SST
+ 120 min	 Vital signs PRISE BPRS VAS POMS Plasma sample
+180 min	 Vital signs PRISE VAS Plasma and Serum sample: 1 ETDA and 1 SST
+ 240 min	 Vital signs PRISE VAS Plasma sample
+ 300 min	 Vital signs PRISE VAS Plasma sample

+360 min	➤ Vital signs
	≻ C-SSRS
	≻ BPRS
	≻ POMS
	≻ PRISE
	> VAS
	> PSS
	➢ Plasma and Serum sample: 1 EDTA and 1 SST
+420 min	➤ Vital signs
	≻ C-SSRS
	> BPRS
	► POMS
	► PRISE
	> VAS
	≻ PSS
	➢ Plasma sample
+480 min	➤ Vital signs
	≻ C-SSRS
	► BPRS
	≻ POMS
	≻ PRISE
	≻ VAS
	≻ PSS
	➢ Plasma sample
Readily for discharge	 Physician assessment followed by decision for discharge
home	 Participants picked up by pre-designated escort home

*Prior to each vital sign, measurement the subject will be resting quietly for a minimum of five minutes before the vital signs are measured. For each specified vital sign time point, two readings will be taken 5 minutes apart and the average of the two readings will be used.

- *a)* Safety parameters for monitoring
 - Psychosis / mental status changes: BPRS, other clinical scales
 - PRISE: nausea, vomiting, diarrhea and other general adverse events
 - Vitals: BP, HR, Temp, Respiration

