Medicine at Mount Sinai, and has volunteered to join us as a Safety Monitor. [name] is the director of the Mount Sinai Diabetes Center and knows T1D very well clinically and in terms of clinical research. In the event of a suspected DLT, [name] along with Drs. [name] and [name] will review the event and make the formal determination of the occurrence of a DLT, which will subsequently inform the CRM and the dose level of the next patients treated in the study.

The DSMC will focus on the following items:

- Study-related adverse events
 - We would like to note that we are also monitoring for adverse events as per our DLT definition (see **Definition of Dose Limiting Toxicity** above).
- Cardiovascular effects: Any of the following that occur after administration of study drug will be considered a cardiovascular effect if temporally related to administration of the investigational intervention and considered at least possibly related to the investigational intervention:
 - Symptomatic hypotension, or > 20% decrease in systolic blood pressure (SBP) from pre-dosing and an absolute SBP < 90; or
 - Symptomatic hypertension, or > 20% increase in SBP or diastolic blood pressure (DBP) from predosing and absolute SBP > 170 or DBP > 95;
 - New onset tachycardia (heart rate >100 bpm) and >20% increase from pre-dosing; or symptomatic bradycardia (heart rate <60 bpm) and >20% decrease from pre-dosing.
 - Signs and symptoms of cardiac ischemia, defined by acute ischemic changes on ECG with or without concomitant symptoms
- Protocol compliance
- Dropouts
- Confidentiality of participants' information
- Other study-specific safety information

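### The protocol gives two incompatible rules for when a fall in heart rate is a DLT, and the choice between them can decide the MTD

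*Combined protocol and SAP*

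**What the plan says.** **Section 4.1, DLT definition, item (d).** Within 6 hours of dosing, bradycardia counts if it is "symptomatic bradycardia (heart rate <60 bpm) and > 20% decrease from pre-dosing". The other vital-sign items can be met on measured values alone. Tachycardia is "New onset tachycardia (heart rate >100 bpm) and >20% increase from pre-dosing". Low blood pressure is "Symptomatic hypotension, or > 20% decrease in systolic blood pressure (SBP) from pre-dosing and an absolute SBP < 90", so its numeric limb stands apart from symptoms, and hypertension is built the same way. The cardiovascular list in the safety-monitoring text repeats the bradycardia wording ("symptomatic bradycardia (heart rate <60 bpm) and >20% decrease from pre-dosing") and refers back to the DLT definition.

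**Section 2.2, Harmine Administration.** A second DLT definition includes the event that blood pressure or "heart rate (HR) changes by greater than 20% relative to baseline values". Just before it, the section anticipates average falls of 18 beats/min in heart rate and 16 mm in blood pressure.

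**Earlier experience.** Background item 4 reports: "With the intravenous administration, on average there was a decrease in pulse rate of 18 beats/minute". Bradycardia and hypotension together capped the intravenous dose at 300 mg. Background item 4 and Section 4.1 both say that oral dosing (20–960 mg) changed neither heart rate nor blood pressure.

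**Data and analysis.** Table 2 schedules vital signs before dosing and at ten post-dose times up to 480 min. At each time "two readings will be taken 5 minutes apart and the average of the two readings will be used". The statistics text describes only the CRM, and Section 5.3 names only AE/SAEs through the CRM and the questionnaires.

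**The concern.** The CRM takes one yes/no per volunteer, so the DLT definition is the primary endpoint. Here two definitions classify the same pulse record differently, in the direction of effect that the protocol itself anticipates.

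If Section 4.1 governs, a large symptom-free fall does not enter the model through item (d), and no other stated analysis would show it by dose. If Section 2.2 governs, the same fall is a DLT and holds escalation back. The dose carried to phase II could then depend on which page the DLT reviewers apply, and a reader of the result could not tell which rule produced it.

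**Working it through.** The plan gives no figure for how often either rule would be met, so there is none to reproduce. Its benchmark is the 25% target DLT rate (Section 4.1).

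**Inputs from the documents.** Eligible resting pulse 60–100 bpm (Section 6.3). Fall of 18 beats/min (Section 2.2; Background item 4). Limits of Section 4.1 (d)(iii): below 60 bpm and a fall above 20%. Limit of Section 2.2: a change above 20%.

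**Step 1: a symptom-free 18 bpm fall at baseline b.**
- Section 2.2 is met if 18/b > 0.20, that is b < 90.
- The numeric limits of Section 4.1 are met if b − 18 < 60, that is b < 78 (the 20% limit then holds too).
- Section 4.1 as written also needs symptoms, so it is not met at any b.

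| Baseline | After fall | Fall | Section 2.2 | 4.1 numeric limits | 4.1 as written |
|---|---|---|---|---|---|
| 60 | 42 | 30.0% | DLT | met | no |
| 70 | 52 | 25.7% | DLT | met | no |
| 75 | 57 | 24.0% | DLT | met | no |
| 78 | 60 | 23.1% | DLT | not met | no |
| 89 | 71 | 20.2% | DLT | not met | no |
| 90 | 72 | 20.0% | no | not met | no |

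**Step 2: share of volunteers below 60 bpm with a fall above 20%.** The documents give no spread, so these are assumptions: baseline normal, truncated to 60–100 bpm, mean/SD 70/8, 75/9 or 80/9; fall normal with SD 5 or 8 bpm. From 400,000 draws (fall SD 5 / SD 8):

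| Mean fall | Baseline 70 | Baseline 75 | Baseline 80 | Range |
|---|---|---|---|---|
| 0 bpm | | | | about 0.1–3.5% |
| 9 bpm | 14 / 23% | 9 / 17% | 6 / 12% | 6–23% |
| 18 bpm | 69 / 62% | 54 / 51% | 39 / 40% | 39–69% |

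**Step 3: can the rule change the selected dose?** An illustrative CRM used Section 4.1's prior toxicity rates (2, 5, 10, 20, 30, 50, 65%), the 25% target, 40 volunteers, a start at 100 mg, no skipping when escalating, and no escalation straight after a DLT. Assumed: the empiric model with a normal prior (mean 0, variance 1.34); baseline pulse mean 70, SD 8, truncated to 60–100; a symptom-free fall proportional to dose with SD 6; 2% DLTs from other causes at every dose; no early stopping. Only falls, not rises, were counted under Section 2.2. There were 500 runs per cell, so a 65% result has a standard error of √(0.65 × 0.35/500) ≈ 2 points.

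| Mean fall at 1200 mg | 4.1 as written | 4.1 numeric limits, symptoms ignored | Section 2.2 |
|---|---|---|---|
| 9 bpm | 1200 mg (96%) | 1200 mg (67%) | 1200 mg (64%) |
| 18 bpm | 1200 mg (95%) | 700 mg (69%) | 700 mg (65%) |
| 27 bpm | 1200 mg (95%) | 500 mg (71%) | 500 mg (60%) |
| 36 bpm | 1200 mg (96%) | 300 mg (79%) | 300 mg (82%) |

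Entries are the dose selected most often, with the percentage of runs. At a mean fall of 18 bpm, Section 2.2 never led to 1200 mg and chose 500 mg in 28% of runs.

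**The case against.** A reader of Section 4.1 alone might infer that a slowed pulse counts in this trial only with symptoms, and that the harm would go unreported. The documents do not support that.

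- Section 2.2 makes any change above 20% a DLT without symptoms. The defect is an unresolved conflict, not a settled symptom-only rule.
- Heart rate is a named safety parameter, and Section 10.1 lets any unfavourable sign be an AE. AEs go on the CRF and to the IRB at annual renewal. However, a symptom-free fall limits no activity, so it would probably be graded mild and miss the moderate-AE route in item (b). Recording it rests on investigator judgement and gives no comparison by dose.
- A reader might also infer that pulse slowing alone limited the intravenous study. It did so together with hypotension, which counts here on numbers without symptoms.
- The only oral evidence reports no pulse change. Section 4.1's own tenfold conversion puts the intravenous doses of 100–300 mg at 1000–3000 mg oral, so only the 1200 mg level reaches that range. A large fall is therefore a possibility, not a prediction. Yet the oral evidence is 11 patients in data that the statistics section itself calls limited and poor, and Section 2.2 carries the 18 bpm figure into this trial.
- Part of the text before the safety-monitoring list was not available, and Section 2.1 says the analysis plan is still to be finalised. The absence of a heart-rate analysis is asserted only for the text available.

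**Conclusion.** The point stands as a conflict between Section 2.2 and Section 4.1 (repeated in the safety-monitoring list), with no stated by-dose analysis of heart rate to show its effect. For a symptom-free 18 bpm fall, the two rules disagree at every eligible baseline from 60 to below 90 bpm; this needs no assumption beyond the documents' figures.

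How much it matters depends on the unknown oral effect. With no mean fall, the numeric limits are seldom met. At a mean of 9 bpm the share lies below the 25% target, and at 18 bpm well above it. In the illustrative CRM, the dose selected most often changes at mean falls of 18 bpm and above, but not at 9 bpm. These shares and dose selections rest on assumed baselines, spreads, prior and dose-response for pulse. They show that the rule can decide the MTD, not that it will. Which rule is clinically right is for the sponsor. This should be corrected, and doing so is cheap.

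**What to change.** 1. **Reconcile** Section 2.2, Section 4.1 (d) and the safety-monitoring list so that one DLT rule, of the sponsor's choosing, feeds the CRM. Section 2.2's blood-pressure wording sits in the same sentence and needs the same treatment.
2. **Add to the statistics section**, from readings already scheduled: (a) a regression of each volunteer's largest heart-rate fall on log dose, adjusted for baseline heart rate, over all treated volunteers, taking the −10 min value as baseline and the readings up to +360 min so that the window matches the 6-hour DLT window; (b) the number at each dose below 60 bpm with a fall above 20%, split by symptoms. Share (b) with the existing DLT reviewers.
3. **Show beside the primary MTD** supportive CRM refits that count, within 6 hours, (i) heart rate below 60 bpm with a fall above 20% regardless of symptoms, and (ii) the Section 2.2 rule, if it is not adopted.

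The cost is protocol wording and a few tables, with no new visits or measurements. A low pulse can be benign in healthy volunteers, so the refits are supportive only and may look less favourable than the primary MTD. With at most 40 volunteers over seven doses, by-dose estimates will be imprecise where few are treated, which is why the pooled regression is included.
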